TITLE	Assessment of wearable sensors during experimental human influenza infection
DESIGN	Human viral challenge study in healthy volunteers
AIMS	
 1. Assess the utility of the Bittium Faros heart rate, physical activity and ECG wearable sensor in measuring changes during influenza infection 2. Assess the utility of the Biovotion Everion heart rate, physical activity and respiratory rate wearable sensor in measuring changes during influenza infection 3. 3. Assess the utility of the Profusa Lumee oxygen sensor in measuring changes during influenza infection 4. Correlate physiological sensor measurements with quantitative measures of viral load and influenza-specific antibodies, B cells and cell-mediated immunity 5. Correlate physiological sensor measurements with results of cognitive tests and questionnaires
POPULATION	Healthy persons aged 18 to 55 years
ELIGIBILITY	Healthy persons aged 18 to 55 years that fit the inclusion and exclusion criteria
DURATION	1 Year

GLOSSARY OF ABBREVIATIONS

AE	Adverse Event
BAL	Bronchoalveolar Lavage
CMI	Cell Mediated Immunity
CRI	Centre for Respiratory Infection
CTL	Cytotoxic T cell
DC	Dendritic Cell
DNA	Deoxyribonucleic Acid
ELF	Epithelial Lining Fluid
FEV ₁	Forced Expiratory Volume in One Second
FI-RSV	Formalin-inactivated RSV vaccine
GC-MS	Gas Chromatography with Mass Spectrometry
GCP	Good Clinical Practice
HA	Haemagglutinin
ICRRU	Imperial Clinical Respiratory Research Unit
LAI	Live Attenuated Influenza Vaccine
NA	Neuraminidase
NHLI	National Heart and Lung Institute
NP	Nucleoprotein
PBMC	Peripheral Blood Mononuclear Cell
PCR	Polymerase Chain Reaction
PEF	Peak Expiratory Flow
PIS	Participant Information Sheet
RSV	Respiratory Syncytial Virus
RV	Rhinovirus

SAE	Serious Adverse Event
SAM	Synthetic Absorptive Matrix
URT	Upper Respiratory Tract
VOC	Volatile Organic Compound
WHO	World Health Organisation

KEYWORDS

Influenza, immune, virus, viral challenge, viral lung disease, infection

INTRODUCTION

1.1. Background to research

Despite the availability of specific antivirals and vaccines, influenza remains one of the greatest causes of morbidity and mortality worldwide. Seasonal influenza affects between 10 and 46% of the population each year with mortality of up to around 12 deaths per 100,000 in developed countries¹. Following the emergence of the pandemic 2009 H1N1 virus (pH1N1), many severe cases also occurred in previously healthy young adults. With every population therefore potentially at risk, the prevention and improved management of seasonal and pandemic influenza are of major continuing importance. This is accentuated by the high cost, variable efficacy and evidence of resistance that limit the usefulness of available antivirals, while current vaccines are poorly effective in their ability to provide long-term protection due to relatively weak immunogenicity and continual virus evolution that leads to immune evasion².

The unpredictability of timing and severity of epidemic and pandemic outbreaks additionally limit the effectiveness of both clinical and public health responses. Recent seasonal outbreaks dominated by H3N2 strains have caused unusually severe disease and unsustainable pressure on health services during winter seasons. Difficulties in ascertaining biomarkers that can predict susceptibility, protection and disease onset or severity have led to major bottlenecks in the improvement of diagnostics, vaccines and therapeutics as well as in patient management. Animal models, which may be informative when used to investigate immune mechanisms involved in immunopathology and protection against influenza (including innate, cell-mediated, and tissue-specific immunity), have been less useful in translation to humans. This has been particularly true when attempting to define physiological responses to infection, which are poorly replicated in animal models where disease is not fully recapitulated.

Recent experience in both natural infection and experimental challenge settings has highlighted the extensive heterogeneity between individuals on exposure to even identical inocula. A proportion of individuals remain completely resistant to infection, while others suffer a spectrum of disease severities from asymptomatic to life-threatening illness. While disease severity usually correlates with higher viral loads, more subtle understanding of the predictors and determinants of severe disease is lacking. Further investigation of the factors that determine why some individuals have minimal symptoms while others suffer severe disease will allow more accurate prediction of risk in individual patients and rational intensification of treatment, as well as identification of new targets for vaccine and therapeutic intervention. If it were possible to predict how severe an influenza-induced illness would be early following exposure, it might be possible to intervene more rapidly with isolation of highly infectious individuals or other public health interventions to prevent onward transmission.

Predicting influenza disease through physiologic monitoring: The wide range of clinical outcomes associated with influenza infection and inability to accurately stratify risk causes difficulties in the care of individual patients as well as management of limited health resources. This is complicated by the late presentation of patients, who generally only seek medical attention once symptoms have become intolerable. One approach to earlier detection of infection would be to identify physiological changes that occur prior to symptom onset that nevertheless predict individuals who go on to symptomatic disease. Previous studies have shown that heart rate variability (HRV) measurements could predict post-stroke infections³ and sepsis^{4,5} up to 60 hours before onset of clinical symptoms. HRV monitoring of high-risk

infants in a neonatal intensive care unit has also been used to predict sepsis and sepsis-like illness and is used in a commercially available HeRO system⁶. While these systems are reliant on continuous monitoring of hospitalised patients using hospital-grade electrocardiogram (ECG) equipment, they provide proof-of-principle that HRV measures can indicate relative risk of infection to guide clinical care and may provide timely warning of pending health changes. The addition of physical activity measures and sleep categorization will provide context to the HRV measures to enable assessment of active, ambulatory subjects. Tissue oxygen measures will aid in the classification of illness severity as oxygen saturation levels have been shown to correlate to with clinical outcomes in respiratory illnesses.

Cognitive changes associated with influenza infection:

Preliminary data suggest that cognitive changes may be detected during episodes of infection. Conversely, social aspects may impact on the response to infection. To investigate these, multiple cognitive testing modalities will be used to assess the subject's cognitive performance at baseline and additional time points throughout the course of influenza infection from flu exposure and recovery. Each instrument has been standardized and evaluated previously⁷⁻⁹. The social support questionnaire is a 27-item quantitative survey questionnaire intended to measure perceptions of social support and satisfaction with that social support¹⁰. The degree of social support has been shown to influence the onset and course of certain psychiatric disorders such as clinical depression¹¹. The Reading the Mind in the Eyes test was originally developed for adults in 1997, to demonstrate the deficits of theory of mind in those with autism spectrum disorders¹². The test involves describing the emotional/mental state of a person based on only an image of their eyes, in a fixed-choice paradigm.

Immune determinants of influenza severity: In animal models, a number of immune factors have been shown to both enhance and ameliorate influenza disease. In particular, the evocative term "cytokine storm" has been used to describe a situation in which inflammatory mediators induce severe life-threatening disease¹³. In mice, pro-inflammatory mediators are highly induced in the lung and contribute to immunopathology following infection with the 1918 H1N1 and avian H5N1 strains¹⁴, but the relative role of soluble mediators in pathogenesis and protection in humans remains unclear. Whether extreme cytokine levels are the cause or effect of severe influenza has been difficult to determine, especially in the absence of samples from directly affected respiratory tissues. Although the respiratory tract is the primary site of influenza infection, easily and consistently accessible peripheral blood may also provide markers by which severity of disease can be predicted. Microarray analysis of whole blood by our collaborators has identified transcriptional signatures that distinguish different respiratory viruses prior to the peak of symptoms¹⁵. Transcriptomic analysis in both this and the nasal compartment are likely to identify signatures associated with infection and disease severity long before the onset of symptoms.

The major surface antigenic determinants of influenza, haemagglutinin (HA) and neuraminidase (NA), both elicit protective humoral responses. However rapid mutation and reassortment of the segmented genome leads to immune escape. Internal viral components, such as the nucleoprotein (NP), which are relatively conserved, do stimulate cross-reactive T cell responses³ but while these may be associated with reduced disease severity, they do not appear to prevent infection with novel strains in the long term. The immune factors that determine whether an individual will develop symptomatic infection following exposure to a respiratory pathogen therefore remain poorly understood. Traditionally, serum antibody has been used as a correlate of protection against influenza and, indeed, high neutralising antibody titres do correlate somewhat with a decreased risk of influenza infection. However, it is clear that antibodies do not explain all aspects of immune protection as some individuals with no detectable neutralising antibody are still protected. Increasing evidence indicates that protective immunity is mediated by a number of factors including early innate immune mechanisms and cell-mediated immunity. Furthermore, these arms of the immune system are interlinked, with innate immunity critically influencing later adaptive responses. Thus a comprehensive understanding of the early innate responses and local mucosal immunity remains a high priority, as well as their association with physiological changes that occur with influenza disease.

Human challenge model at Imperial College London Experimental human infection studies are uniquely capable of addressing questions regarding early events that contribute to immune protection and pathology in influenza but few groups are currently able to carry them out. Additionally, the

controlled in-patient setting of these studies can reduce the variability in responses seen in community-based studies. The UK is world-class in having extensive recent experience using this model. We began conducting experimental human infections with RSV at Imperial College in 2010, with the goal of establishing challenge studies in an academic setting at lower cost, with greater flexibility and increased scientific focus. In 2015, we established the influenza challenge model at Imperial College London and have demonstrated its safety and usefulness in providing unique and consistent data for the study of immunity and immunopathogenesis during acute infection. Our group has now safely challenged >125 participants with respiratory viruses in our centre and are currently the only academic group in Europe with the capacity, experience and skills to conduct these studies. Recently, we have been given access to a new influenza H3N2 challenge strain derived from a 2015 clinical isolate (influenza A/Belgium/4217/2015). Not only does this new challenge agent better reflect recent seasonal outbreaks, but also recent studies have shown a 75% attack rate with moderate but consistent symptomatology. Using this challenge virus in our model will allow questions regarding the capacity of ambulatory physiological sensors to measure the response to influenza infection and how these responses correlate with cognitive and immune outcomes to be addressed.

This study will follow on from our previous Prometheus study, which systematically investigated the early pre-symptomatic period following exposure to influenza in humans and provided exploratory pilot data with non-commercial sensor devices that suggested that sleep disturbance occurred within 24 hours of influenza exposure. The data obtained in this study will be used to test the ability of novel wearable sensors to detect changes associated with infection and disease severity, thus allowing their use in general settings to predict which individuals will go on to more severe symptoms and higher viral shedding, enabling implementation of treatments and other interventions at an earlier stage. Ultimately these data will inform the development of a fully automated, network of human-based wearable sensors that detect biomarkers indicative of respiratory infection and level of severity, and transmit acquired signals to corresponding smartwatches or phones. Current public health networks track only patients who seek medical care. The total time associated with the development of infection symptoms, laboratory-based diagnostic tests, data compilation, and reporting results in a 3–5 week delay in the detection of the disease outbreak. By using human-based, wearable, networked sensors in concert with point-of-care diagnostics and automated data collection and reporting, the time required to detect disease outbreaks may be shortened by weeks. A required innovation is the development of algorithms for illness detection and severity estimation that distinguish host response from confounding factors such as increased mental or physical demands. This study will provide essential data for the development of these algorithms with the acquisition of sensor data from the pre-symptomatic phase of influenza through recovery. The collection of HRV data from multiple sensors will allow for comparison of ECG sensors to wrist and arm sensors that may be more convenient for long-term wear. The integration of physical activity measures will enable evaluation on subjects without activity restrictions.

1.2. Research Hypotheses

1. Novel wearable sensors (i.e, Bittium Faros, Biovation Everion, and Profusa Lumee) can detect physiologic changes that are associated with influenza infection and disease severity.
2. Physiologic patterns of heart rate, physical activity, ECG, respiratory rate and oxygen saturation from wearable sensors can act as biomarkers that enhance current diagnostic practice for early detection of influenza infection and disease prediction.

STUDY OBJECTIVES

1.3. Primary Objective:

- To test the hypothesis that measurements of heart rate, physical activity, ECG, respiratory rate and oxygen saturation can detect influenza infection and disease

1.4. Secondary Objective:

- To identify early signatures using sensor data that predict influenza disease and severity, potentially enabling earlier medical or public health interventions

1.5. Exploratory Objectives:

- To test the associations between physiologic sensor measurements and cognitive function using objective tests
- To test the associations between physiologic sensor measurements and biological and immune readouts

PARTICIPANT ENTRY

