1.17.3. Biovotion Everion sensor

The Biovotion Everion (Figure 2) is a CE marked, non-invasive wearable multi-sensor device that monitors heart rate, skin temperature, respiration rate, steps, activity, and energy expenditure from the skin's surface. It will be attached to the left or right upper arm using an armband and will be in contact with intact skin only. All measurements are taken on the surface of the skin. Data from the device is collected via the Biovotion application, which will be pre-loaded to the mobile device provided. Each participant will have a study user account created with identification only by subject study ID. After successful connection of the sensor and mobile device, study personnel will explain and train subjects on how to use the Biovotion Everion and the features of the Biovotion application as well as ensuring study subjects understand usage, handling and maintaining of the Biovotion Everion. An initial data collection process will be undertaken to check that the Biovotion Everion is working correctly prior to the end of the study visit. The following parameters will be collected: activity, barometric pressure barometer temperature, skin blood perfusion index, blood pulse wave, energy expenditure, galvanic skin response, heart rate, heart rate variability, local temperature, skin temperature, respiration rate, blood oxygenation and steps per day.

Figure 2: Biovotion Everion device, charger/docking station and armband positioning.

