We aim to determine if the different sensors in the study can measure changes associated with influenza infection. For each sensor we will define and compute multiple metrics from the raw sensor output. Each of these metrics will be compared in the healthy versus sick states for each subject. We will consider a metric to be a potential predictor of illness in a single subject if there is a significant ($p < 0.05$) difference between the mean value in the sick and healthy state. Control comparisons will be made by computing the significance of differences between two different healthy periods (e.g. prior to infection and post recovery).

The potential predictors of illness from the within subject analysis will be compared across all subjects to determine if any sensor metrics provide generalizable indicators of illness. A metric will be considered a valid indicator if it is present in at least 85% of the within subject sick/healthy comparisons and less than 25% of the within subject control comparisons. This odds ratio is sufficient to achieve 80% power and a 5% error rate with a sample size of 13 subjects. Based on an established attack rate of 75% with this challenge virus, we estimate that will have 15 of our 20 subjects develop influenza. Therefore, the sample size of this study is sufficient to determine the feasibility of using the selected sensors to measure changes associated with influenza.

Data and all appropriate documentation will be stored for a minimum of 10 years after the completion of the study, including the follow-up period according to Imperial College London policy.

REGULATORY ISSUES

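### The only decision rule has no timing condition and no comparator, so it cannot support or refute hypothesis 2's claim of early detection that enhances diagnosis

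*Combined protocol and SAP*

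**What the plan says.** Section 1.2, hypothesis 2, states that physiologic patterns from the wearables "can act as biomarkers that enhance current diagnostic practice for early detection of influenza infection and disease prediction". The secondary objective (section 1.4) seeks early signatures that predict disease and severity. The sample-size paragraph of Statistics and Data Analysis describes a proof of concept that infection can be detected before symptoms.

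The same section then gives the only decision rule:

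- "Each of these metrics will be compared in the healthy versus sick states for each subject".
- In one participant, a metric is a potential predictor of illness if p < 0.05 for the "difference between the mean value in the sick and healthy state".
- Control comparisons are made by "computing the significance of differences between two different healthy periods".
- Across participants, the metric earns the label of valid indicator when this result holds for "at least 85% of the within subject sick/healthy comparisons and less than 25% of the within subject control comparisons".

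The sick state is not tied to a time, a positive sample or a symptom. The remaining analyses are baseline-versus-infection tests and Spearman correlations. Aim 4 in the synopsis adds correlations of sensor measurements with viral load and immune readouts.

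**The concern.** Enhancing practice and detecting early are claims about order in time or added information relative to something already available. The rule measures neither. It asks only whether a metric differs between two states, and the sick state may include days when the participant already has symptoms and is shedding virus. Physiological change is likely to be easiest to see on exactly those days.

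A metric that responds late could therefore meet the rule and be called a predictor or valid indicator, although it says nothing about the pre-symptomatic phase. The trial would then end without evidence for or against its own early-detection hypothesis, despite collecting diaries and serial lavage that could address it.

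**Working it through.** **1. What the claim needs and what the rule uses.**

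| Needed for early detection or enhancement | In the rule |
|---|---|
| Time of first sensor change | No; a difference in state means |
| Time of first symptom | No |
| Time of first positive viral sample | No |
| Added value over a comparator | No; the comparator is another healthy period |

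The Spearman correlations named in the statistics section concern inflammatory cells, illness severity, viral load and leukocytes. Aim 4 links sensors to viral load, but a correlation of levels does not show which changed first.

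**2. The plan's own figure.** The plan states: "This odds ratio is sufficient to achieve 80% power and a 5% error rate with a sample size of 13 subjects". Inputs: p1 = 0.85, p2 = 0.25, mean 0.55, difference 0.60. Two-sided 5% is assumed because sidedness is not stated for this figure.

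- n = [1.96 × √(2 × 0.55 × 0.45) + 0.842 × √(0.85 × 0.15 + 0.25 × 0.75)]² / 0.60² = (1.379 + 0.472)² / 0.36 = 9.52, so 10.
- Continuity-corrected: (9.52/4) × [1 + √(1 + 4/(9.52 × 0.60))]² = 12.6, so 13.

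The 13 is reproduced when the two sets of comparisons are treated as independent. No input is a time or a diagnostic result, so the figure gives no power for an early-detection or enhancement claim.

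**3. What passing requires.** Expected infected: 20 × 0.75 = 15. The sick limb needs at least 13 of 15 (86.7%; 12 of 15 is 80%). The control limb allows at most 3 of 15 (20%; 4 of 15 is 26.7%). Neither limb depends on when the change occurs.

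**4. Can a late metric pass?** The documents give no effect sizes, so these are assumptions: 15 infected, 24 independent readings a day, 7 healthy days, a sick window of days 1 to 7, a t-test per participant and 300 simulations per case. Each mean rests on 7 × 24 = 168 readings, so the standard error of the difference is √(2/168) = 0.109 SD. Significance needs a difference of about 0.21 SD. A shift starting on day L is diluted to shift × (8 − L)/7.

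| Shift | Onset | Diluted difference | Simulated proportion passing both limbs |
|---|---|---|---|
| 0.5 SD | day 3 | 0.36 | 83% |
| 0.5 SD | day 4 | 0.29 | 14% |
| 0.5 SD | day 5 | 0.21 | 0% |
| 1 SD | day 5 | 0.43 | 99% |

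Late metrics can pass. Whether they do depends on effect size and on how the sick window is drawn, which the plan leaves open.

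**5. Is a lead-time analysis feasible with 15 infected?**

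- Sign test without ties: 12 of 15 leading gives 2 × (455 + 105 + 15 + 1)/32768 = 0.035; 11 of 15 gives 0.118.
- With 4 ties (n = 11): 9 of 11 gives 2 × (55 + 11 + 1)/2048 = 0.065; 10 of 11 gives 2 × (11 + 1)/2048 = 0.012.
- The 4th to 12th ordered lead times give a confidence interval for the median with coverage 1 − 0.035 = 96.5%.
- Table 1 labels lavage as daily but marks it morning and afternoon on days 1 to 5, so its resolution is 12 or 24 hours. If onset is uniform within an interval, the comparator is seen late by half an interval on average, 6 to 12 hours. A near-continuous sensor would gain that lead for free unless put on the same grid.
- If a limit had a 5% false-crossing chance per 12-hour block (an assumption), ten independent blocks would give 1 − 0.95¹⁰ = 40% with at least one false crossing. False alarms must therefore be measured.

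**The case against.** The strongest reply is that the rule was never meant to decide hypothesis 2. It opens with whether sensors can measure changes and closes on feasibility, which fits hypothesis 1 and the primary objective. The plan also calls itself a proof of concept and says larger studies are needed. A reader might infer that a passing metric would be reported as proof that sensors enhance diagnosis. The documents do not say so: nothing links the rule to hypothesis 2, and the hypothesis says only that the patterns can do this. What remains is that no other analysis addresses hypothesis 2. Proof-of-concept status limits generalisability but does not supply a comparator.

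Three further inferences also go too far.

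- **Lavage as current practice.** Section 1.1 describes present care as late and symptom-driven, with sensors working alongside point-of-care tests. Scheduled lavage after a known inoculation is a stricter benchmark. A sensor that lags lavage but precedes symptoms could still help, so first symptom is the primary comparator.
- **Skin temperature left out.** Section 1.17.3 says that the Everion "monitors heart rate, skin temperature, respiration rate, steps, activity, and energy expenditure", and the statistics section allows multiple metrics per sensor. Skin temperature may well be analysed; it is simply not designated as a benchmark.
- **A fixed late-change scenario.** Neither the onset day of a sensor change nor the day of first positive lavage is given, so the simulated cases show possibility, not likelihood.

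**Conclusion.** The point holds in this form: hypothesis 2 and the stated goal concern early detection and added diagnostic value, and nothing planned can support or refute either. A late-changing metric could pass the only rule and be called a valid indicator. On the assumptions above, the chance ranges from 0% (0.5 SD from day 5) to about 99% (1 SD from day 5). Real readings will be correlated, and the sick window is undefined, so these figures are illustrative only.

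The 13-subject figure is not in error for what it covers. The plan should be changed before the data are seen, but the gap does not undermine the test of whether sensors register change during infection.

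**What to change.** Add to Statistics and Data Analysis:

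1. For each infected participant, derive the time of first sensor change past a personal limit set from part of the pre-inoculation data. Name a short list of metrics to contain multiplicity.
2. Report the false-alarm rate of that limit in held-out healthy time and in challenged but uninfected participants (about 20 − 15 = 5, so imprecise). The latter share the move into confinement on day −1, which could itself shift sensor readings.
3. Report the paired lead time (median, 95% CI) primarily against first diary symptom, defined relative to the participant's own baseline, and secondarily against first influenza-positive nasal lavage. Allow for ties and interval sampling, and summarise sensor data on the comparator's 12 to 24 hour grid.
4. State that lavage is tested for influenza, at which times and with what threshold. Section 1.14.3 names RSV for shedding, and Table 1's PCR row, as it reads, marks only two time points.
5. Report Everion skin temperature as a benchmark metric, noting that the documents do not show it to be a validated measure of fever.
6. Claim early detection or enhancement only for metrics that lead the comparator. Otherwise reword hypothesis 2 to detection of changes during influenza infection.

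The cost is plan wording and a small analysis of diaries and samples already scheduled, plus influenza testing of serial lavage if that is not already intended. The downsides are coarse lead times, a lavage comparison stricter than current practice, and the possibility that the enhancement claim is not supported.
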